## PROTOCOL AMENDMENT, BP40950 VERSION 2 RATIONALE

### RATIONALE FOR THE AMENDMENT

[REDACTED], additional clarification regarding the participation of women of non-childbearing potential and the use of contraception has been added ([Section 5.1](#), Inclusion Criteria).

Some inconsistencies in the protocol were also corrected:

- Vital signs - it was specified that temperature could be oral or tympanic ([Section 8.2.2](#))
- Meals and study restrictions – duration of fasting was updated to 10 h instead of 8 h to be consistent with other parts of the protocol ([Section 5.3.1](#))

New text is shown in italics.

# PROTOCOL AMENDMENT, BP40950 VERSION 2

## SUMMARY OF CHANGES

### 1.1 Synopsis

The synopsis has been updated to reflect the changes to the protocol

### 5.1 Inclusion Criteria

#### Sex

##### 6. Male and female participants

The contraception and abstinence requirements are intended to prevent exposure of an embryo to the study treatment. The reliability of sexual abstinence for male and/or female enrollment eligibility needs to be evaluated in relation to the duration of the clinical study and the preferred and usual lifestyle of the participant. Periodic abstinence (e.g., calendar, ovulation, symptothermal, or post-ovulation methods) and withdrawal are not acceptable methods of contraception.

###### a) Female Participants

*Only women of non-childbearing potential (WONCBP) are allowed to be enrolled in this study.*

A female participant is eligible to participate if she is not pregnant (see [Appendix 5](#)), not lactating, and the following condition applies:

- Women of non-childbearing potential, as defined in [Appendix 5](#), who have a negative pregnancy test (blood) within the 28 days prior to the first study drug administration.

*Additional contraceptive measures are only required if menopausal status or non-childbearing potential is not completely certain. In this instance, one of the non-hormonal highly effective contraception methods described in [Appendix 5](#) should be used during the treatment period and for at least 28 days after the last dose of study drug.*

###### b) Male Participants

During the treatment period and for at least 28 days after the last dose of study drug agreement to:

- Remain abstinent (refrain from heterosexual intercourse) or use contraceptive measures such as a condom, with partners who are women of childbearing potential (WOCBP, as defined in [Section 1 of Appendix 5](#)), or pregnant female partners, to avoid exposing the embryo.

- Refrain from donating sperm for at least 28 days after the last dose of study drug.

### **5.3.1 Meals and Dietary Restrictions**

Participants will have to be fasted for at least 4 hours prior to laboratory safety tests at screening and the follow-up visit, and for at least 8 hours prior to laboratory safety tests performed on Day -1 and Day 3.

Consumption of nutrients known to modulate CYP3A activity (e.g., grapefruit or grapefruit juice, Seville orange) will not be permitted within 2 weeks prior to first dosing until the safety follow up visit.

Please note that participants should refrain from consumption of any foods containing poppy seeds within 48 hours (2 days) prior to screening and each admission to the clinical unit to avoid false positive drug screen results.

### **8.2.2 Vital Signs**

Vital signs will include temperature (*oral or tympanic*), systolic and diastolic blood pressure and pulse rate. The vital signs will be measured in a supine position after at least 5 minutes rest at the time point specified in the SoA table ([Section 1.3](#)).

Blood pressure and pulse measurements will be assessed with a completely automated device. Manual techniques will be used only if an automated device is not available. When possible, the same arm should be used for all blood pressure measurements.

## LIST OF ABBREVIATIONS AND DEFINITIONS OF TERMS

Abbreviation	Definition
AE	Adverse event
ALT	Alanine aminotransferase
aPTT	Activated partial thromboplastin time
ASD	Autism spectrum disorder
AST	Aspartate aminotransferase
AUC	Area under the curve
AUC0-inf	Area under the concentration-time curve from time 0 to infinity
BA	Bioavailability
BE	Bioequivalence
BP	Blood pressure
Cavg	Average concentration
Cmax	Maximum serum concentration
CL	Clearance
CL/F	Apparent clearance
CMC	Chemistry manufacturing and control
CNS	Central nervous system
COA	Clinical outcome assessments
CRO	Contract research organization
CSR	Clinical study report
CTCAE	Common terminology criteria for adverse events
DDI	Drug-drug interaction
EC	Ethics Committee
ECG	Electrocardiogram
eCRF	Electronic case report form
EDC	Electronic data capture
EEA	European Economic Area
eCOA	Electronic clinical outcome assessment
ESF	Eligibility screening form
EU	European Commission
FDA	Food and Drug Administration
FSH	Follicle-stimulating hormone
GCP	Good clinical practice
HBsAg	Hepatitis B surface antigen
HBcAb	Total hepatitis B core antibody
HCV	Hepatitis C

HDL	High-density lipoproteins
HIPAA	Health Insurance Portability and Accountability Act
HIV	Human immunodeficiency virus
IB	Investigator's Brochure
ICH	International Council on Harmonisation
IEC	Independent Ethics Committee
IMP	Investigational medicinal product
IND	Investigational New Drug (application)
INR	International normalized ratio
IRB	Institutional Review Board
IRC	Independent Review Committee
IUD	Intrauterine device
IV	Intravenous
LDH	Lactate dehydrogenase
LDL	Low-density lipoproteins
LPLV	Last participant, last visit
LPLO	Last participant, last observation
MAD	Multiple-ascending doses
NOAEL	No-observed-adverse-effect level
NSAESI	Non-serious adverse event of special interest
OTC	Over-the-counter
PD	Pharmacodynamic
PK	Pharmacokinetic
PT	Prothrombin time
QRS	QRS complex
QT	QT interval
QTc	QT corrected for heart rate
QTcF	QT corrected for heart rate using the Fridericia's correction factor
RBC	Red blood cell
RR	RR interval
SAD	Single-ascending dose
SAE	Serious adverse event
SD	Single dose
SoA	Schedule of activities
SOP	Standard operating procedure
SPA	Statistical Programmer
SUSAR	Suspected unexpected serious adverse reactions

TSH	Thyroid-stimulating hormone
ULN	Upper limit of normal
US	United States
V	Volume
V/F	Apparent volume of distribution
WOCBP	Woman of Childbearing Potential
WONCBP	Woman of Non-Childbearing Potential
WBC	White blood cell

## 1. PROTOCOL SUMMARY

### 1.1 SYNOPSIS

**PROTOCOL TITLE:** A 2 PART, RANDOMIZED, OPEN-LABEL, SINGLE DOSE, CROSSOVER STUDY TO ASSESS THE RELATIVE BIOAVAILABILITY OF PHASE II TABLET FORMULATION COMPARED TO THE CURRENT PHASE I CAPSULE FORMULATION AND THE EFFECT OF FOOD AND TASTE ASSESSMENT ON THE PHASE II TABLET FORMULATION IN HEALTHY PARTICIPANTS

**SHORT TITLE** A RELATIVE BIOAVAILABILITY, FOOD EFFECT AND TASTE ASSESSMENT STUDY OF RO7017773 FORMULATIONS

**PROTOCOL NUMBER:** BP40950

[figure not shown]
**VERSION:** 2

**TEST PRODUCT:** RO7017773

**PHASE:** I

### RATIONALE

RO7017773 is a selective gamma-aminobutyric acid type A (GABAA)  $\alpha 5$  subunit-containing receptor positive allosteric modulator. RO7017773 is being developed for the treatment of the two core domains of autism spectrum disorder (ASD): social communication deficits and repetitive behaviors. RO7017773 has the potential to normalize GABAergic signaling in key brain regions implicated in ASD without the side-effects of non-specific GABA modulators (e.g., benzodiazepines).

## **OBJECTIVES AND ENDPOINTS**

		Objectives	Endpoints
Primary			
PART 1	
 
• To assess the relative bioavailability of Phase II tablet formulation compared to Phase I capsule formulation of RO7017773 swallowed whole under fasting conditions following single oral dose administration.
 
		
 
• RO7017773 concentrations and RO7017773 pharmacokinetics (PK) parameters
 

PART 2	
 
• To assess the taste masking of RO7017773 Phase II tablet formulation containing sweetener and flavor dispersed in water and the RO7017773 Phase II tablet formulation without sweetener and flavor dispersed in apple juice.
 
		
 
• Taste questionnaire
 

Secondary			
PART 1	
 
• To assess the PK of RO7017773 Phase II tablet formulation dispersed in water or swallowed whole.
 
• To assess the effect of a high-fat meal on the PK of a single oral dose of RO7017773 Phase II tablet formulation.
 
• To assess the taste of RO7017773 Phase II tablet formulation without sweetener and flavor dispersed in water.
 
	
 
• RO7017773 concentrations and RO7017773 PK parameters
 
• RO7017773 concentrations and RO7017773 PK parameters
 
• Taste questionnaire
 
	
PART 2	
 
• To assess the PK of RO7017773 Phase II tablet formulation containing sweetener and flavor dispersed in water and the RO7017773 Phase II tablet formulation without sweetener and flavor dispersed in apple juice.
 
	
 
• RO7017773 concentrations and RO7017773 PK parameters
 
	
ALL PARTS	
 
• To evaluate the safety and tolerability of single oral doses of different RO7017773 formulations in healthy participants.
 
	
 
• Incidence and severity of AEs.
 
• Changes in vital signs, physical findings, ECG parameters, and clinical laboratory results during and following RO7017773 administration
 
	

## **OVERALL DESIGN**

This is a single-center, randomized, single-dose, open-label, crossover study in healthy participants. The study consists of two parts. Part 1 will enroll 16 participants to assess the performance of the Phase II tablet formulation as compared to the Phase I capsule formulation and a further 8 participants will assess the taste of RO7017773 in Part 2. See below for the details of the dosing regimen in both parts.

## **Study Design**

The primary objective of Part 1 is to determine the relative bioavailability of the two RO7017773 formulations; phase I capsule formulation (Treatment A) and phase II tablet formulation (Treatment B) administered under fasting conditions. The food effect of the RO7017773 Phase II tablet formulation will be explored in Part 1 of the study, in order to understand whether the pharmacokinetic properties of the Phase II tablet formulation of RO7017773 are impacted when administered under fasting or fed conditions (Treatment C). As per the Food and Drug Administration (FDA) Guidance for Industry: Food Effect Bioavailability and Fed Bioequivalence Studies, the test meal provided will be a high-fat and high-calorie meal.

The PK of the Phase II tablet formulation dispersed in water (Treatment D), will be compared with the Phase II tablet formulation swallowed in fasted state. Furthermore, a taste assessment of the Phase II tablet formulation dispersed in water will be conducted (Treatment D).

All participants in Part 1 will receive all four treatments in a randomized, crossover design. Each treatment will be given as a single dose on Day 1 of each Treatment Period.

In Part 2, the taste of the Phase II tablet containing flavor and sweetener dispersed in water will be investigated to understand how the taste is perceived (Treatment A). Additionally, the taste of the Phase II tablet without sweetener/flavor dispersed in apple juice will be assessed (Treatment B). A maximum of eight participants will be enrolled in Part 2 of the study. All participants in Part 2 will receive both treatments in a randomized, crossover design.

The washout period between each dose in both study parts will be at least 7 to 10 days. Participants will have to stay in the clinic from the day before each dosing (Day -1) to Day 3 after dosing for each Treatment Period. Ambulatory visits on Day 4 and Day 5 after each dosing are planned for PK sampling and safety monitoring. Approximately 7 to 14 days after their last dose participants will return to the clinic for a final follow-up visit.

## **Dosing regimen**

Following a screening period of up to 4 weeks participants will receive 4 (Part 1) or 2 (Part 2) single oral doses of RO7017773.

The following treatments will be administered in Part 1 (4 period crossover):

- Treatment A: Phase I capsule swallowed whole under fasted conditions
- Treatment B: Phase II tablet swallowed whole under fasted conditions
- Treatment C: Phase II tablet swallowed whole under fed conditions
- Treatment D: Phase II tablet dispersed in water under fasted conditions (taste assessment)

The following treatments will be administered in Part 2 (2 period crossover) in different participants to Part 1:

- Treatment A: Phase II tablet containing flavor and/or sweetener dispersed in water under fasted conditions (taste assessment)
- Treatment B: Phase II tablet without flavor and/or sweetener dispersed in apple juice under fasted conditions (taste assessment)

The Investigational Medicinal Products (IMPs) are RO7017773 Phase I capsules and Phase II film coated tablets with a dose strength of [REDACTED] mg.

## **Length of Study**

### **Part 1- 4 Period Crossover**

The total duration of the study for each participant will be approximately 9 weeks divided as follows:

- Screening: Up to 4 weeks.
- In clinic periods: Day -1 to Day 3 for each of the 4 treatments.
- Treatment Periods: Day 1 to Day 5 for each of the 4 treatments (with single dosing on Day 1 of each period).
- Washout period 7 to 10 days (washout period is counted from Day 1 dose, i.e., overlapping with treatment period).
- Safety follow-up: 7 to 14 days after last dose.

### **Part 2 – 2 Period Crossover**

The total duration of the study for each participant will be approximately 7 weeks divided as follows:

- Screening: Up to 4 weeks.
- In clinic Periods: Day -1 to Day 3 for each of the 2 treatments.
- Treatment Periods: Day 1 to Day 5 for each of the 2 treatments (with single dosing on Day 1 of each period).
- Washout period 7 to 10 days (washout period is counted from Day 1 dose, i.e., overlapping with treatment period).
- Safety follow-up: 7 to 14 days after last dose.

## **End of Study**

A participant is considered to have completed the study if he/she has completed all treatment periods within Part 1 or Part 2 and the safety follow-up visit.

The end of the study is defined as the date when the last participant last observation (LPO) occurs. LPO is expected to occur approximately 2 weeks after the last participant's last dose.

## **PARTICIPANT POPULATION**

The participants of this study are healthy participants between 18 and 55 years of age.

### **Inclusion/Exclusion Criteria**

#### **Inclusion Criteria**

Participants are eligible to be included in the study only if all of the following criteria are met at screening and Day -1.

#### **Informed Consent**

1. Able and willing to provide written informed consent and to comply with the study protocol according to International Council on Harmonisation Good Clinical Practice (ICH-GCP) guidelines and local regulations.

#### **Age**

2. Participants 18 to 55 years of age inclusive, at the time of signing the informed consent.

## Type of Participants and Disease Characteristics

3. Non-smoker for at least six months.
4. Healthy, as judged by the Investigator.

Healthy status will be defined as the absence of evidence of any active or chronic disease following a detailed medical and surgical history, a complete physical examination, vital signs, 12-lead ECG, hematology, blood chemistry, serology and urinalysis.

## Weight

5. Body mass index (BMI) within the range 18 to 32 kg/m^2 (inclusive).

## Sex

6. Male and female participants

The contraception and abstinence requirements are intended to prevent exposure of an embryo to the study treatment. The reliability of sexual abstinence for male and/or female enrollment eligibility needs to be evaluated in relation to the duration of the clinical study and the preferred and usual lifestyle of the participant. Periodic abstinence (e.g., calendar, ovulation, symptothermal, or post-ovulation methods) and withdrawal are not acceptable methods of contraception.

### a) Female Participants

*Only women of non-childbearing potential (WONCBP) are allowed to be enrolled in this study.*

A female participant is eligible to participate if she is not pregnant, not lactating, and the following condition applies:

- Women of non-childbearing potential who have a negative pregnancy test (blood) within the 28 days prior to the first study drug administration.

### b) Male Participants

During the treatment period and for at least 28 days after the last dose of study drug agreement to:

- Remain abstinent (refrain from heterosexual intercourse) or use contraceptive measures such as a condom, with partners who are women of childbearing potential, or pregnant female partners, to avoid exposing the embryo.
- Refrain from donating sperm for at least 28 days after the last dose of study drug.

*Additional contraceptive measures are only required if menopausal status or non-childbearing potential is not completely certain. In this instance, one of the non-hormonal highly effective contraception methods described in [Appendix 5](#) should be used during the treatment period and for at least 28 days after the last dose of study drug.*

## **Exclusion Criteria**

Participants are excluded from the study if any of the following criteria are met at screening and Day -1.

### **Medical Conditions**

1. Any condition or disease detected during the medical interview/physical examination that would render the participant unsuitable for the study, place the participant at undue risk or interfere with the ability of the participant to complete the study, as determined by the Investigator.
2. History or evidence of any medical condition potentially altering the absorption, metabolism or elimination of drugs. This includes a surgical history of the gastrointestinal tract affecting gastric motility or altering the gastrointestinal tract.
3. History or evidence of any medical condition that potentially may alter the taste sensory perception including ageusia and dysgeusia.
4. History of any clinically significant gastrointestinal, renal, hepatic, bronchopulmonary, neurological, psychiatric, cardiovascular, endocrinological, hematological or allergic disease, metabolic disorder, hypofertility, cancer or cirrhosis
5. Use of any psychoactive medication, or medications known to have effects on CNS or blood flow taken within 30 days prior to first dosing (or within 5 times the elimination half-life of the medication prior to first dosing, whichever is longer).
6. History of convulsions (other than benign febrile convulsions of childhood) including epilepsy, or personal history of significant cerebral trauma or CNS infections (e.g. meningitis).
7. A history of clinically significant hypersensitivity (e.g., drugs, excipients) or allergic reactions.
8. Any major illness within one month before the screening examination or any febrile illness within one week prior to screening and up to first study drug administration.
9. Abnormal blood pressure, defined as confirmed (based on the average of  $\geq 3$  consecutive measurements at screening and Day -1) systolic blood pressure (SBP) greater than 140 or less than 90 mm Hg, and diastolic blood pressure (DBP) greater than 90 or less than 50 mm Hg.
10. Abnormal pulse rate, defined as confirmed (based on the average of  $\geq 3$  consecutive measurements at screening and Day -1) resting pulse rate greater than 100 or less than 40 bpm.
11. History or presence of clinically significant ECG abnormalities before study drug administration (e.g. PQ/PR interval  $> 210$  ms, QTcF  $> 450$  ms) or cardiovascular disease (e.g. cardiac insufficiency, coronary artery disease, cardiomyopathy, congestive heart failure, family history of congenital long QT syndrome, family history of sudden death).
12. Clinically significant abnormalities in laboratory test results (including hepatic and renal panels, complete blood count, chemistry panel and urinalysis). In the case of uncertain or questionable results, tests performed during screening may be repeated before randomization to confirm eligibility.

13. ALT and/or bilirubin  $> 1.5 \times \text{ULN}$  (isolated bilirubin  $> 1.5 \times \text{ULN}$  is acceptable if bilirubin is fractionated and direct bilirubin  $< 35\%$ ).
14. Current or chronic history of liver disease, or known hepatic or biliary abnormalities (with the exception of Gilbert's syndrome or asymptomatic gallstones).
15. Participants who, in the Investigator's judgment, pose a suicidal or homicidal risk, or any participant with a history of suicidal or homicidal attempts.

#### **Prior/Concomitant Therapy**

16. Have used or intend to use over-the-counter or prescription medication including herbal medications within 30 days prior to dosing. Specific medications listed under permitted medications will be allowed.
17. Participants likely to need concomitant medication during the study period (including for dental conditions).

#### **Prior/Concurrent Clinical Study Experience**

18. Participation in an investigational drug or device study within 90 days prior to screening, as calculated from the day of follow-up from the previous study, or more than 4 participations in an investigational drug or device study within a year prior dosing.

#### **Diagnostic Assessments**

19. Positive test for drugs of abuse or alcohol.
20. Show evidence of human immunodeficiency virus (HIV) infection and/or positive human HIV antibodies.
21. Presence of hepatitis B surface antigen (HBsAg) or positive hepatitis C antibody test result at screening or within 3 months prior to starting study treatment.

#### **Other Exclusions**

22. Dietary restrictions that would prohibit the consumption of standardized meals.
23. Inability or unwillingness to fully consume standardized breakfast at Day 1 (for Part 1, Treatment C only).
24. Consumption of any prohibited food and beverages before study start and during the study.
25. Any suspicion or history of alcohol abuse and/or suspicion of regular consumption of drug of abuse or previous history of or treatment for a dependence disorder.
26. Sensitivity to any of the study treatments, or components thereof, or drug or other allergy that, in the opinion of the Investigator, contraindicates the participation in the study.
27. Participants who have donated over 500 mL of blood or blood products or had significant blood loss within 3 months prior to screening.

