## **5.2 EXCLUSION CRITERIA**

Participants are excluded from the study if any of the following are met at screening and Day -1:

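### Exclusion criterion 27 (donation over 500 mL or significant blood loss) stops at screening, so it does not cover the 2 to 28 days before the first dose: a minor participant-protection gap

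*Protocol*

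**What the plan says.** Criterion 27 appears under Other Exclusions in the synopsis (Protocol Section 1.1) and again in Section 5.2, with the same text: "Participants who have donated over 500 mL of blood or blood products or had significant blood loss within 3 months prior to screening".

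The synopsis says when the criteria apply: "Participants are excluded from the study if any of the following criteria are met at screening and Day -1". Section 5.2 has the same lead-in: "Participants are excluded from the study if any of the following are met at screening and Day -1". The Schedule of Activities (Section 1.3, Table 5) accordingly places an eligibility review at screening and on Day -1.

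The synopsis gives the time from screening to dosing: "Following a screening period of up to 4 weeks participants will receive 4 (Part 1) or 2 (Part 2) single oral doses". Tables 1 and 3 in Section 1.2 set screening at Day -28 to Day -2 for both parts.

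Some other criteria run through to dosing. Criterion 8 excludes "any febrile illness within one week prior to screening and up to first study drug administration". Criterion 21 applies its hepatitis tests "at screening or within 3 months prior to starting study treatment".

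**The concern.** A donation or blood-loss criterion excludes on history alone, without waiting for an abnormal test result. Its purpose is to avoid adding study blood sampling to a recent loss. The days that matter most for that purpose are those just before dosing, and these are the days that criterion 27 leaves out. Read literally, it excludes a volunteer who donated almost three months before an early screening visit and passes one who donated the week before admission.

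Participants then give pharmacokinetic samples up to Day 5 of each period, over four periods in Part 1 and two in Part 2, and also give safety bloods. What is at stake is the protection of an individual participant and, at most, an unrepresentative pre-dose blood count for that person.

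**Working it through.** The plan states no figure on this point, so the check is a reading of the text plus a day count.

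**1. Length of the gap.** Inputs: screening on Day -28 to Day -2 (Protocol Section 1.2, Tables 1 and 3), first dose on Day 1, and the SAP Section 9.2.3 rule that a pre-dose study day is the measurement date minus the first dose date. Day -28 is therefore 28 days before the dose and Day -2 is 2 days before it.

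| Screening day | Days from screening to first dose (outside criterion 27) | Share of the last 91 days before dosing |
|---|---|---|
| Day -28 | 28 | 28/91 = 31% |
| Day -2 | 2 | 2/91 = 2% |

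The share counts calendar days. It is not the chance that anyone is affected. Participants are resident from Day -1, so the time in which an outside donation could happen is about one day shorter: 28 - 1 = 27 days at most and 2 - 1 = 1 day at least.

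**2. The literal consequence.** Take screening on Day -28 and three months as 90 days. A donation of over 500 mL made 90 days before screening was made 90 + 28 = 118 days before the dose, and it excludes. The same donation on Day -2 was made 2 days before the dose, and it falls outside the criterion.

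**3. Whether the Day -1 review closes the gap.** On Day -1 the question put to the participant is unchanged: was there such a donation or loss in the three months before screening? The answer cannot change between the two reviews. A site may treat the second review as extending the window, but the text does not say so.

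**4. Whether another rule covers it.**
- Section 5.3 restricts diet, caffeine, alcohol, tobacco and exercise, but not donation. No other section mentions donation or blood loss as grounds for exclusion.
- Exclusion criterion 1 needs a detected condition plus a judgement: "Any condition or disease detected during the medical interview/physical examination that would render the participant unsuitable for the study".
- Exclusion criterion 12 needs an abnormal result: "Clinically significant abnormalities in laboratory test results (including hepatic and renal panels, complete blood count, chemistry panel and urinalysis"). Haematology is repeated on Day -1, so a marked fall would be seen.
- Inclusion criterion 4 (healthy on history, examination and haematology) must also hold on Day -1.
- Section 7.2 lets the investigator withdraw a participant whose circumstances raise the risk.

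These act on a clinical finding or on judgement. A recent donor with an unremarkable examination and an acceptable count can pass all of them.

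**The case against.** The strongest reply is that the gap is narrow. To enter, a participant must pass screening, then donate over 500 mL or lose a significant amount of blood, then present on Day -1 with an acceptable count and examination, and not be judged unsuitable. That stands, and it limits the weight of the point. A reader might infer that nothing in the plan would exclude such a person. The documents do not support that, because the provisions listed above would catch some of them.

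A second reply is that the anchor is not an anomaly. The 90-day limit in criterion 18 and the major-illness limit in the first half of criterion 8 also stop at screening. That stands too. The protocol mixes both anchors, so this is an improvement in wording and not the repair of an internal contradiction.

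A reader might also infer harm to the analysis: a depressed haematology baseline followed by recovery over the periods, read as a drug effect. The documents do not support this as a threat to treatment comparisons. SAP Section 17.1.3 summarises laboratory data descriptively by treatment and scheduled time, and SAP Section 9.4.3 plans no hypothesis testing. Day -1 haematology is scheduled in each period, so drift would be visible. In the Part 1 Williams square each treatment occurs once in every period, so a time trend is not tied to one formulation. Nothing shows an effect on the pharmacokinetic ratios.

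Nor can the combined blood burden be judged. The sampling detail is not in the public text, so no volume is relied on here.

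**Conclusion.** The gap is real and minor. Criterion 27 itself does not reach a donation of over 500 mL or a significant blood loss in the 2 to 28 days between screening and first dose, and the Day -1 review does not extend it. The other safeguards are partial: they should find a participant with a clinically evident loss, but not reliably a donor with an acceptable blood count.

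The conclusion rests on a literal reading of the criterion, which is complete and identical in both places, and on the stated screening window. How often the situation would arise is not given; it is likely to be rare. No estimate, confidence interval or sample size depends on it. It is an optional correction.

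**What to change.** In criterion 27, in both the synopsis and Section 5.2, keep the three-month look-back from screening and extend the window through to first study drug administration, using the closing phrase of criterion 8's febrile-illness clause. Ask about donation and blood loss since screening at the Day -1 eligibility review.

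The cost is one phrase in two places and one question at a review that already takes place. The downside is that a rare volunteer who donates after screening is deferred or lost.

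A ban on donation until follow-up is not needed to close this gap. It concerns the on-study period, and the consent pages, which might already address it, are not in the public text.
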